## **Introduction**

Asymptomatic bacteriuria (AB) is a condition in which bacteria from the bowel are detected in significant numbers by culture of a specimen of collected urine, but the patient does not have urinary-specific symptoms or signs.[1] In contrast, urinary tract infection (UTI) is the presence of bacteria in urine specimens with defined symptoms or signs.[2, 3] The use of inappropriate antibiotic treatment for AB is a systemic stewardship problem, causing harm due to antibiotic adverse effects, selection of bacteria toward drug resistance, and wasted cost.[4]

Recognizing the inappropriate treatment of AB to be a concern among long term care (LTC) residents, [name], [name] and colleagues performed an observational study in St. John's.[5] 101 consecutive positive urine cultures submitted from six LTC facilities were included, and nurses were interviewed regarding reasons for collection, antibiotic treatment given, and patient response to treatment after seven days. In most cases, basic investigations such as vital signs and urinalysis were not performed. The rate of positive cultures was the same as the expected AB rate. Most considered reasons for urine collection did not correlate with positive culture. Physicians did not treat according to culture results, and treatment did not correlate with improvement in activities of daily living score. The conclusion was that urine culture may not be a useful investigation in LTC, and that changes were required in the selection of patients for testing and antibiotic treatment decisions.

Because urine represents half of all specimens received in Eastern Health microbiology laboratories, with 30 percent of specimens requiring bacterial identification and antibiotic susceptibility testing, significant cost savings may be realized by improvements in policy, so further research is being proposed.

## Literature Review

UTI's are among the commonest indications for antimicrobial therapy, among inpatients, outpatients and LTC patients. Prevalence of AB varies from 1-5% among healthy premenopausal women, to 25-50% among women in LTC, to 100% among patients with chronic indwelling catheters.[6] Treatment of AB with antimicrobial therapy does not reduce incidence of symptomatic UTI, complications or death, and is associated with adverse events.[7] Among women with AB randomized to treatment, resistance to antibiotics among isolated bacteria increased.[8] Even among pregnant women, the treatment of AB may not provide significant benefit.[9, 10]

Various interventions have been proposed to reduce inappropriate antibiotic treatment for AB. Physicians have difficulty avoiding treatment when presented with positive culture results. A cluster randomized trial of an algorithm for diagnosis and treatment of UTI failed to reduce urine culture collection rate.[11] 169 residents and staff physicians demonstrated poor knowledge of published AB treatment guidelines, suggesting education may be of benefit.[12] Prospective audit and feedback to physicians reduced treatment duration, but not treatment initiation decisions in one study,[13] and reduced culture orders and treatment during and after an intervention period in another study.[14] An educational intervention reduced inappropriate treatment during the intervention period.[15] Audit and educational interventions require considerable effort and may not lead to sustainable change.

A novel approach to inappropriate therapy changes the way urine culture results are provided to physicians. In a pilot study, non-catheterized inpatients with positive urine cultures were reported by the microbiology laboratory with a general statement suggesting the physician call the lab if specific culture information was considered clinically necessary.[16] This provided

a barrier to access to positive culture results. In the intervention group (415 specimens, 17.8% culture positive, 2% had clinical evidence of UTI), restricted reporting reduced inappropriate therapy from 48% to 12%, with no incidence of UTI or sepsis. Among 37 positive cultures reported in the restricted way, only 5 calls were received to the laboratory requesting complete culture report. The study used retrospective and catheterized control groups.

The use of restricted reporting could provide a cheap and sustainable intervention to reduce inappropriate treatment for AB. Because the study was not randomized, the estimate of true effect may be biased. An ideal design would include randomization of positive cultures between restricted and standard reporting.

### **Research Objectives**

Research Question: Among inpatients with positive urine cultures reported by Health Sciences microbiology laboratory, would restricted reporting, as compared to standard reporting, lead to a reduction in the rate of inappropriate antibiotic therapy without an increase in UTI or pyelonephritis (kidney infection)?

Primary efficacy outcome: proportion of inappropriate antibiotic therapy prescribed by physicians based on published diagnostic criteria for AB and UTI [2, 4, 17] in an intention to treat population. Inappropriate therapy is defined as any treatment for AB, or no treatment for UTI, or treatment for UTI to which the isolated bacteria is resistant.

Primary safety outcome: proportion of untreated UTI and untreated bacteremia.

Secondary efficacy outcomes: proportion of calls from physicians requesting complete report, drug cost savings based on reduction in treatment.

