### **Methodology**

The proposed study is a randomized trial of two methods of laboratory reporting in which physicians are the main research participants. At the time of positive urine culture results, the patient will be randomized by computer generated random number placed into serially numbered sealed, opaque envelopes in two equal groups. One group will receive restricted reporting, with a report that states "This POSITIVE urine culture may represent asymptomatic bacteriuria or urinary tract infection. If urinary tract infection is suspected clinically, please call the microbiology laboratory at [name] between 0900 to 2300, or the microbiology technologist on-call at [name] at night, for identification and susceptibility results." The other group will receive conventional reporting of identification and susceptibility. Physicians will then have the option of calling the laboratory to receive the results or not. Complete results will be released by telephone and Meditech to physicians who call to request them. Physicians will be informed about the study prior to initiation, and debriefed about the study after the results have been collected.

Inclusion criteria will include consecutive positive urine cultures collected from adults in acute care that are greater than or equal to 18 years of age. Inpatients must be admitted to Health Sciences Center or St. Clare's Mercy hospitals only, in order to facilitate access to inpatient records. Exclusion criteria will include pregnancy, antibiotic treatment at the time of collection, collection from an indwelling urinary catheter, patients in the Intensive Care Unit and patients with blood neutrophils  $<1.0$  within 7 days, which will help protect immunocompromised individuals. Furthermore, [name] will review patient charts at 24 and 72 hours and 7 days after collection to ensure patients experience minimal adverse events.

After randomization and reporting, a physician investigator will assess inpatients for the true diagnosis of AB or UTI. Health records will be accessed including demographics, treatment

decisions and outcomes (untreated UTI or pyelonephritis). Frequency of physician calls requesting complete reporting will be recorded.

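### The primary safety outcome counts only untreated infections, so a UTI treated solely with a drug the isolate resists falls outside it

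*Combined protocol and SAP*

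**What the plan says.** Research Objectives defines inappropriate therapy, the primary efficacy outcome, as "any treatment for AB, or no treatment for UTI, or treatment for UTI to which the isolated bacteria is resistant". The next statement is "Primary safety outcome: proportion of untreated UTI and untreated bacteremia". The protocol nowhere defines *untreated*. Methodology uses the same narrow term when it describes what will be taken from health records: "decisions and outcomes (untreated UTI or pyelonephritis".

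The restricted report (Methodology) opens with "This POSITIVE urine culture may represent asymptomatic bacteriuria or urinary tract infection". It then asks a physician who suspects UTI to telephone the laboratory "for identification and susceptibility results". The control arm receives identification and susceptibility in the ordinary way.

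**The concern.** The intervention discloses one fact and holds back another. The physician learns that the culture is positive but, without a call, does not learn which organism grew or which drugs it resists. A physician who suspects UTI may treat empirically, not call, and leave the patient on a drug that does not work. The efficacy definition recognises this event; the safety outcome does not.

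The research question asks for less inappropriate therapy with no increase in UTI or pyelonephritis, and Implications says the results may support restricting access to urine culture. If ineffective treatment of true UTIs rose in the restricted arm, the safety comparison would not show it, and that comparison would lean toward finding no harm. The efficacy outcome would include the events, but pooled with AB treatment, and the plan does not call for its components to be reported.

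**Working it through.** **1. The two definitions side by side**

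| Event | Efficacy outcome | Safety outcome (plain reading) |
|---|---|---|
| AB, any antibiotic | counted | not applicable |
| UTI, no antibiotic | counted | counted |
| UTI, only an antibiotic the isolate resists | counted | not counted |
| Bacteremia, no antibiotic | not named | counted |
| Bacteremia, only an antibiotic the isolate resists | not named | not counted |

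The third row is the gap. Because the efficacy definition names "treatment for UTI to which the isolated bacteria is resistant" separately from no treatment, *untreated* in the next sentence most naturally means no antibiotic at all.

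**2. The plan's own figure**

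The sample size concerns efficacy only: 45% against 15%, two-sided 5% error, 80% power. With a pooled proportion of 0.30:

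n = [1.960 × √(2 × 0.30 × 0.70) + 0.842 × √(0.45 × 0.55 + 0.15 × 0.85)]² / 0.30² = 35.4 per arm.

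Continuity correction: (35.4/4) × [1 + √(1 + 4/(35.4 × 0.30))]² = 41.8, so 42 per arm and 84 in total, as stated. The increase to 100 equals 84/(1 − 0.16). Nothing in this calculation uses the safety outcome, so redefining that outcome leaves the sample size unchanged.

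**3. How many events could be missed**

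Inputs from the pilot study (Literature Review): 415 specimens, 17.8% culture positive, 2% with clinical evidence of UTI, and 5 calls for 37 restricted reports. From the sample size paragraph: 100 patients, so 50 per arm.

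- Positives: 0.178 × 415 = 73.9. UTIs: 0.02 × 415 = 8.3. Share: 8.3/73.9 = 11.2%, assuming that both percentages refer to the 415 and that every UTI was culture positive.
- UTIs in the restricted arm: 0.112 × 50 = 5.6.
- Excess in the restricted arm = U × (1 − c) × r. Here U is the number of UTIs, c the share of them for which the physician calls, and r the chance that the empirical drug is one the isolate resists. This assumes that every UTI is treated, that a call corrects any mismatch, and that control physicians correct every mismatch.

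The documents give neither c nor r. Taking r = 0.10 to 0.30 as an assumption:

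| U | c | Excess events |
|---|---|---|
| any | 1 | 0 |
| 5.6 | 5/37 = 0.135 | 0.5 to 1.5 |
| 15 (assumed) | 0.135 | 1.3 to 3.9 |

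The rows with c = 0.135 apply the call rate for all restricted positives to true UTIs. The pilot does not show that this is right: 37 × 0.112 = 4.2 expected UTIs, against 5 calls. That is compatible with a call for every UTI, which is the first row.

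**4. Whether the composite can hide the events**

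Take 22/50 efficacy events in the control arm, all AB treatment, and 5/50 in the restricted arm before any mismatched UTI (illustrative counts). Fisher's exact test, two-sided:

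| Mismatched UTIs added to restricted arm | Restricted | Control | p |
|---|---|---|---|
| 0 | 5/50 | 22/50 | 0.0002 |
| 4 | 9/50 | 22/50 | 0.009 |
| 6 | 11/50 | 22/50 | 0.03 |

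Even with six such events, more than the range in step 3, the trial would report a significant benefit and the safety outcome would record none of them.

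**The case against.** The strongest reply is that the harm is not invisible. A mismatched UTI counts against restricted reporting in the efficacy outcome. Charts are reviewed at 24 hours, 72 hours and 7 days, and physicians of discharged patients are contacted at 7 days about adverse events. The records item in Methodology can also be read as capturing any pyelonephritis, which is a clinical consequence of ineffective therapy. All this stands, and it lowers the severity. It does not supply a count of ineffectively treated UTIs by arm, and step 4 shows that the composite cannot stand in for one.

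Three stronger readings are tempting, and the documents do not support them.

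- A reader might infer that ineffective treatment is the harm restricted reporting is most likely to cause. The protocol ranks no harms. Its statement of benefits and risks names possible untreated UTI as the risk to patients, which the safety outcome does count. Mismatch needs a longer chain: UTI suspected, treated, no call despite the request to call, a resisted drug chosen, and no later change.
- A reader might take the pilot report that "only 5 calls were received to the laboratory requesting complete culture report", from 37 restricted results, to mean that most true UTIs would go without a susceptibility result. That rate covers all restricted positives. The report invites calls when UTI is suspected, so calls should concentrate among UTIs.
- A reader might extend the mechanism to bacteremia. Only the urine report is restricted, and nothing says blood culture susceptibilities are withheld. The wording gap exists for bacteremia, but the causal route through its blood isolate is not shown.

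Control patients may also be mismatched before their results arrive. What matters is the difference between arms, which the documents do not allow anyone to estimate.

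**Conclusion.** The gap in wording is real. It rests on the plain reading of an undefined term, not on an explicit scoring rule, and the lack of a definition itself needs correcting. The safety comparison would miss a plausible harm of the intervention and, if that harm is commoner in the restricted arm, would be biased toward no harm. The size is unknown. The excess could be near zero if physicians call whenever they suspect UTI, or a few events among 50 restricted patients under the less favourable assumptions in step 3. Few as they are, such events would bear directly on the safety claim. The primary efficacy analysis is unaffected. Confidence is high in the definitional gap and low in any figure for its effect. Severity: should-fix.

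**What to change.** Define the primary safety outcome as the proportion with UTI, or with bacteremia where isolate susceptibility is available, without active treatment: either no antibiotic, or only antibiotics to which the isolate is resistant. State the window over which this is judged; the existing 7-day chart review would serve. The window must be fixed in advance because a patient who starts on a resisted drug and is switched within it would count as actively treated. Report the no-treatment and resistant-treatment components separately by arm. Leave the efficacy definition and the sample size unchanged.

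The cost is small. For UTI, treatment and urine-isolate susceptibility are already needed to score efficacy, so no new data are required. For bacteremia, blood-isolate susceptibility would have to be retrieved, and the protocol does not say that it is collected. The safety event rate may be slightly higher than under the present wording. The change concerns how outcomes are counted and alters no patient's care.

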The microbiology laboratory at Health Sciences Center receives 130 urine specimens per day, with 30 percent reported as significant growth (40 specimens per day). Twenty-five percent are submitted from inpatients. Method of collection will be determined prior to randomization. Study data collection and analysis will take place at the microbiology laboratory only.

The research hypothesis is that restricted reporting will reduce the rate of inappropriate treatment prescribed by physicians. Among inpatients, the expected rate of inappropriate treatment in the control group will be 45 percent, and 15 percent in the intervention group. Accepting a risk of type 1 error of five percent, and a risk of type 2 error of twenty percent, the study will recruit 84 patients. In order to account for missing data, recruitment will be increased to 100 patients. This will require approximately ten days of recruitment. The statistical test to be used is a comparison of proportions between two groups (T test, two sided analysis). Because true diagnosis may be biased by lack of access to clinical information, an intention to treat analysis including all patients randomized will be performed.

Physicians must remain unaware of the research project so that their treatment decisions are unbiased. However, a general notice will be sent to all physicians regarding the study design, and a debrief will be provided in which study results are presented and the option to withdraw data will be provided. This will cause physicians to feel less deceived while still not informing them of the study and thus will not change their behavior.

Physicians of discharged inpatients will be contacted at 7 days to assess for adverse events. Because recruitment will be brief, it is unlikely that physicians will have a second patient in the study.

Ethics permission will be sought from the local ethics board. Consent of patients or physicians will not be requested. In compliance with TCPS requirements, participants will experience no more than minimal risk. [name] who will assess inpatient charts at 24 and 72 hours and 7 days to surveil adverse events. If an adverse event occurs, the patient will be removed from the study immediately and given standard treatment. Physician consent will not be requested, as awareness of the study would bias treatment decisions.

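### The safety outcome counts only untreated infection, so a patient classed as asymptomatic bacteriuria who progresses after the report and is then treated is not counted, although the research question asks about any increase in infection

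*Combined protocol and SAP*

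**What the plan says.** Under Research Objectives, the research question asks whether inappropriate therapy falls "without an increase in UTI or pyelonephritis (kidney infection"). The same section then defines the only safety endpoint, the primary safety outcome, as the "proportion of untreated UTI and untreated bacteremia". It gives no time at which untreated is judged, no onset rule and no denominator.

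Under Methodology:
- Allocation follows the culture result: "At the time of positive urine culture results, the patient will be randomized". The physician investigator's diagnosis of AB or UTI comes after randomization and reporting.
- The record abstraction covers treatment "decisions and outcomes (untreated UTI or pyelonephritis"). Bacteremia is not in that list.
- For surveillance, an investigator "will review patient charts at 24 and 72 hours and 7 days after collection", and physicians of discharged patients are contacted at 7 days.
- On adverse events: "If an adverse event occurs, the patient will be removed from the study immediately and given standard treatment".

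**The concern.** The question is about how often infection occurs. The endpoint is about how often infection goes without treatment. Withholding a report could do harm through delay: an infection is recognised late, progresses, is found and is then treated. That sequence raises incidence without necessarily adding an untreated case. Because the plan provides for treatment once an adverse event is found, better surveillance moves more progressions out of the endpoint.

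At stake is whether the trial can answer its own safety question. The Literature Review describes the earlier pilot's safety result as no occurrence of UTI or sepsis, which is an incidence measure. A count limited to untreated cases is not directly comparable with it. Patients enter without consent on a minimal-risk basis, which makes a clear safety measure more important.

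**Working it through.** **The plan's own figure.** No safety rate, margin or power is stated, so none can be reproduced. The sample size sets the arm size. With 45% v 15%, two-sided alpha 0.05 and 80% power:
- Uncorrected: n = [1.960·√(2·0.30·0.70) + 0.842·√(0.45·0.55 + 0.15·0.85)]² / 0.30² = 35.4, so 36 per arm.
- Continuity-corrected: (35.4/4)·[1 + √(1 + 4/(35.4·0.30))]² = 41.8, so 42 per arm and 84 in total, as stated.
- 84/(1 − 0.16) = 100, so about 50 per arm after the allowance for missing data.

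**Patient paths under the plain wording.**

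| Path | Untreated UTI? | Untreated bacteremia? | Inappropriate therapy (efficacy)? |
|---|---|---|---|
| AB, untreated, no progression | no | no | no |
| AB, untreated; progresses after the report; detected and treated | no | no | no, since leaving AB untreated is appropriate |
| UTI from the start, untreated early; progresses; then treated | depends on when untreated is judged | no | depends on the same point |
| UTI, never treated | yes | only if bacteremic | yes |
| Bacteremia before randomization, never treated | only if classed as UTI | yes | only if classed as UTI |

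The second row is the gap. It stays open whatever scoring time is chosen for untreated UTI at the initial classification. The third row is closed by a defined scoring time.

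**Illustration for the second row.** The counts k and the treated fraction f are assumptions; the documents give neither. If k of 50 patients in an arm progress from AB to bacteremia, the incidence is k/50 and the expected rate counted as untreated bacteremia is k(1 − f)/50.

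| k | Incidence | f = 0.5 | f = 0.9 | f = 1.0 |
|---|---|---|---|---|
| 1 | 2% | 1% | 0.2% | 0% |
| 2 | 4% | 2% | 0.4% | 0% |
| 3 | 6% | 3% | 0.6% | 0% |
| 5 | 10% | 5% | 1.0% | 0% |

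**What a full count could show.** For 2/50 v 0/50, the two-sided Fisher p is 2·C(50,2)/C(100,2) = 2·1225/4950 = 0.495. For 0/50, the exact two-sided 95% upper limit is 1 − 0.025^(1/50) = 7.1%.

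**The case against.** The strongest defence is that the outcome has two components, and the harm restricted reporting is most likely to cause is a missed UTI, which one of them names. A true UTI left untreated at the 24 h or 72 h review could be scored as untreated UTI before later treatment, and as inappropriate therapy in the efficacy outcome. The Literature Review also cites evidence that treating AB does not reduce symptomatic UTI, complications or death, so few AB patients may progress because a report was withheld. Adverse events are watched for at three chart reviews and a 7-day contact, so treated progressions would not go unseen.

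Much of this stands. A reader might infer that two treated bacteremias against none would be reported as 0 v 0, or that nearly all post-report bacteremias are invisible. The documents do not support that: cases that began as untreated UTI could still be counted, surveillance could record the rest, and a high treated fraction is an assumption.

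A reader might also infer that bacteremia present before the report distorts the outcome and must be excluded. It can be counted if untreated, since there is no onset rule and existing bacteremia is not among the exclusions. But randomization balances it in expectation, and withholding the report could still affect whether it is treated. Excluding such patients could hide that effect.

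Finally, a reader might infer that a low safety count alone would be used to justify restricting access. The Implications section links rarity of untreated infection to more selective urine collection; restriction is a separate, conditional statement that depends on agreement with the previous study.

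What the defence does not answer is the AB patient who progresses and is treated. Surveillance may note the case, but the plan defines no comparison of such cases between arms.

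**Conclusion.** The concern holds in this limited form: the safety question is about incidence, the safety endpoint is not, and treated progression from AB falls outside every outcome compared between arms. For UTI present from the start, counting is indeterminate until a scoring time is fixed.

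The size cannot be derived from the documents. Under assumed counts of 1 to 5 progressions per 50, a true 2% to 10% contributes 0% if all are treated and 1% to 5% if half are. The conclusion rests on the plain meaning of untreated and on the adverse-event rule being followed. Correcting it changes what the trial can describe, not its power: even a fully counted 2 v 0 is far from a significant difference, and no events in 50 would still be compatible with a rate of up to 7.1%. The sample size is unaffected.

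**What to change.** - Add a safety outcome compared by randomized arm: new symptomatic UTI, pyelonephritis or bacteremia with onset after randomization and up to the 7-day review, counted whether or not treated. Bacteremia with a positive blood culture drawn before randomization is not counted as new.
- Keep untreated UTI and untreated bacteremia as a separate component, and state when untreated is judged and the denominator.
- Add bacteremia to the outcomes abstracted from health records, so that Research Objectives and Methodology agree.
- State that patients removed after an adverse event stay in the safety analysis. The removal sentence needs to be reconciled with the Methodology statement that all randomized patients are analysed.
- Present the comparison descriptively, with counts and exact confidence intervals by arm.

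No new exclusion is needed, and no rule on treating patients changes.

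The cost is slightly more abstraction, including blood-culture dates, and a possibly less favourable safety count. The three chart reviews and the 7-day contact already provide the follow-up. Because the chart reviews run from collection, the window after randomization is 7 days minus the time to the positive result, and the report should say so.
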